12.8.3. Exploratory Endpoints and Methods

12.8.3.1. Investigator-Assessed PFS

Investigator-assessed PFS is defined as time from randomization until disease progression (assessed by the Investigator per IWCLL 2008 criteria) or death from any cause, whichever occurs first.

Analysis methods for Investigator-assessed PFS will be similar to those described for PFS as assessed by the IRC.

12.8.3.2. Investigator-Assessed ORR

Investigator-assessed ORR will be summarized and analyzed similarly to IRC-assessed ORR.

12.8.3.3. Improvement of Disease-related Symptoms

Disease-related symptoms including weight loss, fatigue, fever, night sweats, abdominal pain due to splenomegaly, or anorexia) will be assessed by at each assessment compared to baseline. Percentage of patients with improvement will be compared using χ^2 test.

12.8.3.4. Patient-Reported Outcome (PRO) Measures

Patient Reported Outcome (PRO) measures include EORTC QLQ-C30 and EQ-5D-5L.

For EORTC QLQ-C30, change in scores from baseline to each assessment will be summarized.

For EQ-5D-5L, change in weighted utility score from baseline to each assessment will be summarized. The scores for the five categorical dimensions will be used to compute a single utility score ranging from zero (0.0) to one (1.0) representing the general health status of the patient. The United Kingdom weights will be used to generate patient utilities from the 5 dimensions.

12.8.3.5. Biomarker Analysis

Analyses are to identify biomarkers that are predictive of response (or resistance) to ibrutinib. Analyses will be performed within each treatment group in total and stratified by clinical covariates or molecular subgroups. The associations of biomarkers with clinical response or time-to-event endpoints will be assessed using the appropriate statistical methods (analysis of variance [ANOVA], categorical, or survival model), depending on the endpoint. Correlation of baseline expression levels or changes in expression levels with response or time-to-event endpoints will identify responsive (or resistant) subgroups.

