3.3. Exploratory Objectives

To evaluate and compare between the two treatment arms in terms of:

- To evaluate Investigator-assessed PFS and ORR per IWCLL 2008 criteria
- To evaluate improvement and/or resolution of disease-related symptoms
- To evaluate PRO by European Organisation for Research and Treatment of Cancer Quality of Life Questionnaires Core 30 (EORTC QLQ-C30) and EuroQoL Five-Dimension (EQ-5D-5L)
- To evaluate medical resource utilization (MRU)
- To determine the PK characteristics of ibrutinib in patients with CLL/SLL and to determine which, if any, covariates (eg, age, gender, body size, race) influence exposure to ibrutinib

- To investigate potential predictive biomarkers and mechanisms of resistance for the disease

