7.1.26. Genetic and Molecular Prognostic Markers

A blood sample will be collected and analyzed centrally to study the pretreatment prognostic factors. These prognostic factors have previously been associated with disease outcome in CLL patients.

IgVH and p53 Mutational Status

One sample will be collected to study leukemia cell immunoglobulin heavy-chain variable (IgVH) and p53 mutational status.

CD38 and ZAP-70 Leukemia Cell Expression

One sample will be collected to study the leukemia cell expression of CD38 and ZAP-70.

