11.3. Exploratory

- Investigator-assessed PFS per IWCLL 2008 criteria
- Investigator-assessed ORR per IWCLL 2008 criteria
- Improvement of disease-related symptoms (weight loss, fatigue, fever, night sweats, abdominal pain due to splenomegaly, or anorexia).
- Patient reported outcomes (PRO) as measured by EORTC QLQ-C30 and EQ-5D-5L.
 - The efficacy measure for the EORTC QLQ-C30 will be the change in scores from baseline to each assessment for all scales.

- The efficacy measure for the EQ-5D-5L will be the change in weighted utility score from baseline to each assessment.
- Medical resource utilization (MRU) associated with the therapy including the number of hospitalizations, emergency department visits, blood product transfusions, and use of hematopoietic growth factors.
- PK characteristics of ibrutinib in patients with CLL/SLL and to determine which, if any, covariates (eg, age, gender, body size, race) influence exposure to ibrutinib.
- Exploratory evaluation of predictive biomarkers and/or mechanisms of resistance.

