12. STATISTICAL CONSIDERATIONS

This section outlines statistical analysis approaches and methods for the study. Specific details for efficacy and safety analyses will be described in the Statistical Analysis Plan (SAP).

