12.6.4. Biomarker Population

Biomarker population includes patients whose biomaterial is available and who have consented to participate in the study's biomarker evaluation.

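### The biomarker plan seeks markers predictive of ibrutinib response through within-arm associations, which do not by themselves separate predictive from prognostic baseline markers

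*Protocol*

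**What the plan says.** Protocol 12.8.3.5 states the aim: "Analyses are to identify biomarkers that are predictive of response (or resistance) to ibrutinib". It then gives the structure of the analysis: "Analyses will be performed within each treatment group in total and stratified by clinical covariates or molecular subgroups". Methods are to suit the endpoint (analysis of variance, categorical or survival models). The rule for drawing conclusions is: "Correlation of baseline expression levels or changes in expression levels with response or time-to-event endpoints will identify responsive (or resistant) subgroups".

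The status is exploratory. Protocol 3.3 lists the objective "To investigate potential predictive biomarkers and mechanisms of resistance for the disease", and 11.3 lists the matching endpoint. The analysis set in 12.6.4 is a subset of unstated size: "Biomarker population includes patients whose biomaterial is available and who have consented".

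Among the samples taken are tests for IgVH and p53 mutation status and for CD38 and ZAP-70 expression. Protocol 7.1.26 says of these: "These prognostic factors have previously been associated with disease outcome in CLL patients".

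Section 12 of the protocol defers detail to the SAP. The supplied SAP covers only the final analysis and has no biomarker section. Its one between-arm subgroup item, in Table 1, is a forest plot of PFS hazard ratios. The subgroups are not defined and no interaction test is named.

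**The concern.** A prognostic marker shifts outcome whatever the treatment. A predictive marker changes the size of the treatment effect, so the evidence for it is a treatment-by-marker interaction. An association found among ibrutinib patients is compatible with either kind. Under the protocol's rule, such an association is enough to name a responsive or resistant subgroup.

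The risk is concrete because the trial collects markers that the protocol itself describes as prognostic. These are the ones most likely to correlate with outcome on ibrutinib for reasons unrelated to the drug. What is at stake is the wording of the biomarker conclusions and any later development that relies on them. The primary and secondary comparisons are not affected.

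**Working it through.** **The plan's own figure.** The documents give no figure for the biomarker analysis. The only sizing statement (Protocol 12.3) is about 90% power with 176 PFS events, hazard ratio (HR) 0.6 and two-sided 0.05, with one interim analysis at about 117 events.

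- Schoenfeld, fixed design: |ln 0.6| × √176 / 2 = 3.388; Φ(3.388 − 1.96) = 92.3%.
- Freedman, fixed design: √176 × 0.4/1.6 = 3.317; Φ(3.317 − 1.96) = 91.3%.
- Two-look Lan-DeMets O'Brien-Fleming design at 117/176 = 0.665 (bounds 2.514 and 1.993): 92.1% and 91.0% respectively, or 90.7% and 89.8% if a futility bound of the same type is obeyed.

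The stated power is reproduced. The point below does not depend on it.

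**Inputs from the documents.** At least 350 patients, 1:1 (Protocol 4); HR 0.6; 117 and 176 PFS events.

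**Assumptions not in the documents.** Binary marker with 50% prevalence, marker data on all 350 patients, exponential PFS, the same marker HR in both arms (so no interaction), and marker HR 1.5 or 2.

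**Events per arm.** With 175 patients per arm, solve 175(1 − e^(−h)) + 175(1 − e^(−0.6h)) = D, where h is the cumulative control hazard.

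- D = 117: about 70.5 events on ofatumumab and 46.5 on ibrutinib.
- D = 176: about 103.4 and 72.6.

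**Chance of a significant association within one arm.** Φ(ln(HR) × √d / 2 − 1.96) plus the negligible opposite tail, where d is the events in that arm. For HR 2 and d = 46.5: 0.693 × 6.82 / 2 = 2.363, and Φ(0.403) = 66%. Significance on ibrutinib only is p₁(1 − p₂), with p₁ for ibrutinib and p₂ for ofatumumab. At D = 117 and HR 1.5 this is 0.282 × (1 − 0.398) = 17%.

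The simulated values come from 2,000 trials per setting, with Cox Wald tests within each arm and a test of the difference between arms. Monte Carlo standard error is about 1 percentage point near 62%.

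| PFS events | Marker HR | Significant on ibrutinib: formula / simulated | Ibrutinib only: formula / simulated | Interaction test, simulated |
|---|---|---|---|---|
| 117 | 1.5 | 28% / 27% | 17% / 17% | 4% |
| 117 | 2 | 66% / 62% | 11% / 11% | 4% |
| 176 | 1.5 | 41% / 40% | 19% / 18% | 5% |
| 176 | 2 | 84% / 82% | 5% / 4% | 5% |

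**Sensitivity.** At HR 2.5 the simulated within-ibrutinib rate is 86% (117 events) and 96% (176). At 30% prevalence and HR 2 it is 65% and 83% simulated (58% and 77% by formula). Because the biomarker subset may hold fewer events, the formula was also run for 40, 60 and 90 ibrutinib-arm events: 25%, 35% and 49% at HR 1.5, and 59%, 77% and 91% at HR 2.

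**Power of the interaction test.** The standard error of the log ratio of HRs is √(4/d₁ + 4/d₂). At 117 events it is √(4/46.5 + 4/70.5) = 0.378, so for a true ratio of 2, Φ(0.693/0.378 − 1.96) = 45%. At 176 events it is 0.306, giving 62% (63% simulated). For a ratio of 3, power is about 81–83% and 95%.

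**The case against.** Several stronger readings are tempting, and the documents do not support them.

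A reader might infer that the control arm goes unused, so that prognostic and predictive markers cannot be told apart and prognostic ones are certain to be mislabelled. But the analysis is planned in each treatment group. A purely prognostic marker would tend to show up on ofatumumab as well, which is an informal check. That check has no stated rule, and comparing significance between arms is not a valid test of a difference. The 4–18% in the table is what remains after it.

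A reader might also count every disagreement in significance between the arms as mislabelling. Under the same formula, significance on ofatumumab only is p₂(1 − p₁), or 15–32% across the four settings, and the two directions together reach 20–51%. Most of that total is the ofatumumab-only pattern, which arises because that arm has more events. It is not a marker labelled predictive of response to ibrutinib.

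Part of the aim is properly a within-arm question. Protocol 7.1.27 describes comparing patients with different outcomes to find mechanisms of primary or later resistance. Acquired resistance and on-treatment changes in expression are not baseline interaction questions.

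Finally, the endpoint is exploratory, Section 12 is an outline, and the freedom to choose an appropriate model does not exclude an interaction term. A separate biomarker plan may exist, so it is not established that no interaction analysis was intended. However, Protocol 12.8.3.7 points to a separate plan for population pharmacokinetics, whereas 12.8.3.5 points to none. Exploratory status lowers the stakes, but it does not make a within-arm association evidence that a marker is predictive.

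**Conclusion.** The concern holds in a limited form. For baseline markers, the rule in Protocol 12.8.3.5 does not by itself support the word predictive, and it may label a prognostic marker as predictive. For a purely prognostic marker with HR 1.5 to 2, the chance of a significant association on ibrutinib is about 27–62% at 117 events and 40–82% at 176, against about 5% for an interaction test. With an informal side-by-side reading of the arms, the ibrutinib-only pattern still appears in about 4–18% of trials.

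These sizes rest on the assumed prevalence, marker HR, event split and complete marker data. The documents supply none of these, and the true rates depend on the marker's prognostic strength and on the events in the biomarker subset. No primary or secondary conclusion changes. This is a worthwhile, inexpensive improvement to an exploratory analysis.

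**What to change.** Amend Protocol 12.8.3.5, or the biomarker analysis plan if there is one, as follows.

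- For each baseline marker, fit one model across both randomised arms (Cox for PFS, logistic for response) with treatment, marker and their interaction, accounting for the two randomisation factors. Call a marker predictive only on the interaction estimate and its confidence interval.
- Report within-arm results as associations with outcome.
- Keep acquired-resistance and on-treatment-change analyses within the ibrutinib arm, and label them as such.
- Use PFS and response as the main endpoints. Treat any OS interaction with caution: ofatumumab patients could receive ibrutinib (Protocol 7.3.4), and SAP Table 1 does not censor OS at that point, so the contrast is diluted. SAP Table 1 also counts investigator-assessed PFS regardless of crossover, so later PFS cuts call for the same care.
- If a separate biomarker plan exists, cite it in 12.8.3.5.

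The cost is a few sentences and some extra models on data already collected. The drawback is limited power: about 45% at 117 events and 62–63% at 176 for a ratio of HRs of 2, and less if the biomarker subset is smaller. A non-significant interaction would therefore not rule out a predictive effect, and the result stays exploratory. The minimum alternative is to drop the word predictive and describe the findings as associations with outcome on each treatment.

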12.8.3.6. Medical Resource Utilization (MRU) Associated with the Therapy

Parameters collected for MRU associated with the therapy include number of hospitalizations, number of emergency department visits, number of blood product transfusions, and number of use of hematopoietic growth factors. Those parameters will be summarized with descriptive statistics by treatment arm.

12.8.3.7. Pharmacokinetic (PK) Analysis

The plasma concentration data for ibrutinib will be summarized using descriptive statistics at each timepoint. Population PK analysis of plasma concentration-time data of ibrutinib will be performed using nonlinear mixed-effects modeling. Data may be combined with data from other studies to support a relevant population PK model. Available patient characteristics (eg, demographics, laboratory variables, genotypes, etc.) will be tested as potential covariates affecting PK parameters. Details will be given in a population PK analysis plan and the results of the population PK analysis will be presented in a separate report.

12.9. Safety Analyses

Safety summaries will include tabulations in the form of tables and listings. The safety analysis will be conducted using the safety population. Patients will be analyzed according to the actual treatment received.

Study drug exposure including duration and dosage as well as dose modifications of study drug including dose reduction, dose delay, missed doses, and dose interruption will be summarized.

12.9.1. Adverse Events (AEs)

Adverse events (AEs) will be graded by the Investigator according to the NCI CTCAE v4.0 for non-hematological AEs. Hematologic toxicity will be assessed by the IWCLL 2008 criteria for grading hematologic toxicity in CLL studies. Verbatim descriptions of AEs will be coded using the current version of the Medical Dictionary for Regulatory Activities (MedDRA). Adverse events that started from the date of the first dose of study drug up to 30 days after the date of the last dose of study drug are considered treatment-emergent. All-treatment emergent AEs will be summarized by treatment arm. The incidence rates of treatment-emergent AEs will be summarized by System Organ Class (SOC), preferred term, toxicity grade, and relationship to study drug. In addition, SAEs, Grade 3 or above AEs, AEs leading to study treatment discontinuation, delay, reduction, or interruption, AEs leading to death, and events of special interest will be summarized. Multiple occurrence of the same event in a given patient will be counted once at the maximum severity and strongest relationship to study drug.

AEs leading to death and non-fatal SAEs will be listed by patient and tabulated by preferred term.

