9.2. Definitions

9.2.1. Adverse Events

An AE is any untoward medical occurrence in a patient administered a pharmaceutical product and which does not necessarily have a causal relationship with this treatment. An AE can therefore be any unfavorable and unintended sign (including a clinically significant abnormal laboratory finding, for example), symptom, or disease temporally associated with the use of an investigational study drug, whether or not considered related to the study drug ([ICH-E2A, 1995](#)).

For the purposes of this clinical study, AEs include events which are either new or represent detectable exacerbations of pre-existing conditions.

Disease progression is not an adverse event; rather it may be the cause of an adverse event. The clinical diagnosis that is associated with disease progression must be reported as all other adverse events. “Disease progression” should never be used as an adverse event term.

Adverse events may include, but are not limited to:

- Subjective or objective symptoms spontaneously offered by the patient and/or observed by the Investigator or study staff including laboratory abnormalities of clinical significance.
- Any AEs experienced by the patient through the completion of final study procedures.
- AEs not previously observed in the patient that emerge during the protocol-specified AE reporting period, including signs or symptoms associated with CLL/SLL that were not present before the AE reporting period (see [Section 9.3.1](#))
- Complications that occur as a result of protocol-mandated interventions (eg, invasive procedures such as biopsies).

The following are NOT considered AEs:

- **Pre-existing condition:** A pre-existing condition (documented on the medical history CRF) is not considered an AE unless the severity, frequency, or character of the event worsens during the study period.

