9.3.1. Adverse Event Reporting Period

All adverse events will be reported from the time the patient signs the Informed Consent Form until 30 days following the last dose of study drug.

If an SAE is present at the End-of-Treatment Visit, the SAE should be followed to resolution or until the Investigator assesses the patient as stable, or the patient is lost to follow-up or withdraws consent. Resolution/stable means the patient has returned to baseline state of health or the Investigator does not expect any further improvement or worsening of the event.

If a death occurs within 30 days after the last dose of study drug, the death must be reported to the Sponsor as an SAE.

Any SAE that occurs more than 30 days after the last dose of the study drug and is deemed related to ibrutinib, must be reported to the sponsor.

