9.3.2. Assessment of Adverse Events

Investigators will assess the occurrence of AEs and SAEs at all patient evaluation timepoints during the study. All AEs and SAEs whether volunteered by the patient, discovered by study personnel during questioning, detected through physical examination, clinically significant laboratory test, or other means will be recorded in the patient's medical record and on the AE CRF and, when applicable, on the SAE Worksheet.

Each recorded AE or SAE will be described by its duration (ie, start and end dates), severity, regulatory seriousness criteria (if applicable), suspected relationship to the investigational product, and any actions taken.

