## **5. SAFETY ASSESSMENTS**

Safety data will be summarized for the safety population.

Adverse events will be coded by system organ class and preferred term according to the Medical Dictionary for Regulatory Activities (MedDRA). Severity of AEs will be graded by the investigator according to the National Cancer Institute-Common Terminology Criteria for Adverse Events (NCI-CTCAE) v4.0 for non-hematological AEs and iwCLL 2008 guidelines for hematologic toxicity.

Treatment-emergent adverse events (TEAE) are all reported AEs from the first dose of the study drug, through the treatment phase and up to 30 days after the last dose of the study drug or initiation of subsequent anticancer therapy, whichever came first. TEAE SAEs, TEAE non-SAEs and TEAE leading to death will be summarized by treatment arm.

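### Treatment-emergent status has no worsening clause, so an AE that starts before first dose and worsens on drug can be missing from the protocol's treatment-emergent tables and the SAP's final AE summaries

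*Protocol*

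**What the plan says.** **Collection.** Protocol 9.3.1 starts AE reporting at consent: "All adverse events will be reported from the time the patient signs the Informed Consent Form". Protocol 4 allows a Screening Phase of up to 28 days before first dose. Sections 7.3.1 and 7.3.2.1 list AEs among the assessments at Screening and again before the Week 1 dose.

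**Recording.** Protocol 9.3.2: "Each recorded AE or SAE will be described by its duration (ie, start and end dates), severity", followed by seriousness, relationship and action taken. Protocol 9.2.1 adds that "AEs include events which are either new or represent detectable exacerbations of pre-existing conditions". It describes a pre-existing condition as one documented on the medical history form.

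**Classification.** Protocol 12.9.1 treats as treatment-emergent "Adverse events that started from the date of the first dose of study drug", with the window closing 30 days after the last dose. SAP 5 defines TEAEs as "all reported AEs from the first dose of the study drug", running to 30 days after the last dose or the start of subsequent anticancer therapy, whichever is earlier.

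**Tables.** Protocol 12.9.1 plans the main tables for treatment-emergent AEs: "The incidence rates of treatment-emergent AEs will be summarized by System Organ Class (SOC), preferred term, toxicity grade, and relationship to study drug". It then continues: "In addition, SAEs, Grade 3 or above AEs, AEs leading to study treatment discontinuation, delay, reduction, or interruption, AEs leading to death". The same sentence also covers special-interest events. It also plans a by-patient listing and a preferred-term tabulation of fatal AEs and non-fatal SAEs. SAP 5 names three AE summaries by arm: serious TEAEs, non-serious TEAEs and fatal TEAEs.

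**The concern.** Worsening on drug of an event that was already present is something a safety comparison should capture. Take a moderate infection that begins a few days before first dose and becomes severe or fatal two weeks into treatment. Its start date precedes dosing, so a rule based on start date does not count it, whatever happens later. If one drug aggravates such events more than the other, the difference between arms in TEAEs is understated. Safety and tolerability is a stated secondary comparison (Protocol 3.2 and 11.2).

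The result can also depend on which form the site uses. If the infection goes on the AE form, its worsening may stay within the same record. If it is added when medical history is updated before the Week 1 dose (Protocol 7.3.2.1), Protocol 9.2.1 makes the worsening an AE. That update can take place after randomization in an open-label trial, when the site knows the arm.

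**Working it through.** No arithmetic applies. The check follows one test case through each planned output: an AE starts after consent and before first dose, and becomes higher grade, serious or fatal on drug within the window.

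1. **Is the event in the database?** Yes. Collection begins at consent (Protocol 7.1.4 and 9.3.1).
2. **Does its worsening create a new record?** The documents do not say. Section 9.3.2 lists what describes an AE but gives no rule for one that is ongoing and changes grade. The exacerbation wording in 9.2.1 is tied to pre-existing conditions, described there as conditions on the medical history form.
3. **Which outputs contain it?** That depends on the answer to step 2:

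| Planned output | Limit stated | One record, pre-dose start | New record dated on drug |
|---|---|---|---|
| Protocol: tables by SOC, preferred term, grade, relationship | Treatment-emergent only | Excluded | Included |
| Protocol: serious, Grade 3 or higher, treatment-change, fatal and special-interest summaries | None stated | Not excluded by the wording | Included where the category applies |
| Protocol: tabulation of fatal AEs and non-fatal SAEs | None stated | Not excluded by the wording | Included where the category applies |
| SAP: serious, non-serious and fatal TEAEs | TEAE only | Excluded if the definition is onset-based | Included in the matching table, unless it begins after subsequent anticancer therapy |

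4. **Which document governs?** Protocol 12 leaves the specific details of the safety analyses to the SAP, and SAP 1 says that the SAP describes the final analysis. The SAP row therefore matters most for the final report, and every AE summary it names is limited to TEAEs.
5. **Do the documents agree on the serious and fatal tables?** Not in wording. The protocol states no treatment-emergent limit for them, and the SAP does.

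**The case against.** A reader might infer that such an event appears in no planned AE table. Protocol 12.9.1 does not support that. Severe, serious and fatal AEs each have a summary there with no stated treatment-emergent limit, and fatal AEs and non-fatal SAEs have a separate tabulation. These summaries follow the treatment-emergent sentences and could be meant as subsets of them, but the text does not say so.

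A reader might also infer that every fatal case of this kind is lost. That too goes beyond the text. Section 9.3.1 requires a death within 30 days of the last dose to be reported as an SAE, and 9.3.3 asks for the cause of death as the AE term. The protocol's table of fatal AEs can therefore hold the case. Loss is possible at most from the SAP's fatal-TEAE summary, and only if the report carries the pre-dose start date.

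Other points on this side carry some weight:

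- SAP 5 does not use the word started, so a wider reading is open. But without a stated date rule, onset is the natural reading, and it matches the protocol.
- The exacerbation wording and the Week 1 medical-history update will bring in some worsened events. Neither requires a new record for an AE first recorded after consent.
- The form-completion guidelines mentioned in Protocol 13.7 may set a rule for worsening. They are not part of these documents.
- Exclusion criterion 15 removes some patients with an uncontrolled infection before dosing.
- The laboratory shift tables in Protocol 12.9.2 show laboratory worsening without reference to AE onset, so the gap falls mainly on clinical events.
- The SAP covers only the final analysis. The report of the primary analysis was completed in March 2014, and any plan that governed it is not among these documents.

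**Conclusion.** The concern holds in a limited form. The treatment-emergent definition in Protocol 12.9.1 rests on start date alone, and SAP 5 adds no worsening clause. An AE that begins between consent and first dose, keeps one record and worsens on drug is excluded from the protocol's treatment-emergent tables. It is also excluded from the SAP's three final-analysis summaries if SAP 5 is read as onset-based. It is not excluded by the wording of the protocol's serious, Grade 3 or higher and fatal AE summaries or its tabulation of deaths and SAEs.

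The conclusion rests on two assumptions: that SAP 5 means onset, and that sites did not open a new on-drug record at worsening. The documents give neither the rate of pre-dose AEs nor the share that worsen, so the number of patients affected and the effect on the arm difference cannot be derived. The primary efficacy result is not touched. The change is still worth making, because the present rule can omit on-drug worsening from the final safety summaries and the correction is small.

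**What to change.** 1. In Protocol 12.9.1 and SAP 5, define a TEAE as an AE that starts in the stated window, or one that started before first dose and increases in grade, becomes serious or becomes fatal within that window.
2. Take the date of worsening from AE and SAE follow-up records. Protocol 9.3.3 requires follow-up information for SAEs, which should supply dates for serious and fatal cases. Where an ongoing pre-dose AE has no dated grade change, list it separately. Do not classify it by its maximum grade, because a record that holds only the maximum does not show when it was reached.
3. State how the worsening of an AE already recorded after consent is to be entered.
4. State in both documents whether the serious, Grade 3 or higher and fatal AE tables cover all AEs or TEAEs only.

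The cost is a few sentences and some extra programming. No new data collection is needed, provided that cases without a dated grade change go to the separate listing. The downside is slightly higher TEAE counts in both arms.
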